9.1.5. Severity

The investigator is to define the severity of each AE using the following definitions as a guideline. The investigator will consider the range of the possible severity of the event and identify the severity that is the most appropriate according to her/his medical judgment.

Mild – Awareness of signs or symptom, but easily tolerated

Moderate – Discomfort, enough to cause interference with usual activity

Severe – Incapacitating with inability to perform usual activity.

9.1.6. Relationship to study medication

The investigator will determine if there is a reasonable causal relationship between the study medication and an AE or not. The investigator will use her/his best medical judgment and consider all relevant factors (*e.g.*, temporal relationship, location of the event, the subject's relevant medical history, concomitant therapies and concurrent conditions) to determine the relationship of the AE to the study medication. The investigator will define the relationship of an AE to the study medication by selecting one of the following categories:

Related – There is a reasonable causal relationship between the study medication and the AE.

Not Related – There is not a reasonable causal relationship between the study medication and the AE.

The expression “reasonable causal relationship” is meant to convey in general that there are facts (evidence) or arguments to suggest a causal relationship (International Conference on Harmonization [ICH] E2A).

9.2. Reporting Procedures

9.2.1. Procedures for reporting adverse events

At each post-enrollment visit, the investigator will question the subject to elicit AEs using a non-directive question such as “Has there been any change in your health since the previous study visit?” If appropriate, based on the subject’s response to non-directed questioning to elicit AEs, the investigator will follow-up with directed questions and appropriate evaluations.

Any AE noted during the reporting period must be reported in the source documents and on the appropriate AE eCRF. AEs that are defined as “Not Related” to the study medications will be followed until they are resolved or until the subject’s last study visit. AEs that are defined as “Related” to the study medications will be followed until they are resolved or, if not resolved after the subject’s last study visit, until in the opinion of the investigator, the AE reaches a clinically stable outcome with or without sequelae.

9.2.2. Procedure for reporting a serious adverse event

Upon becoming aware of a SAE occurring during the AE reporting period, whether or not related to the study medications, the investigator must:

1. Take the appropriate medical action to ensure the subject’s safety.
2. Immediately inform the Safety Monitor of the SAE by email, ensuring that the subject information is deidentified (only subject initials and subject number) to:
 - **ProPharma, Email:** [contact].
 - **[contact]**
3. Print a copy of the email confirmation from ProPharma and place in the study file.
4. Within 24-hours complete, as fully as possible, an AE eCRF and an SAE form; e-mail the forms and any other relevant information (e.g., concomitant medication eCRF, medical history eCRF, laboratory test results) to ProPharma (Aclaris Therapeutics, Inc. Safety Monitor).
5. Monitor and document the progress of the SAE until it resolves or, if not resolved after the subject’s last study visit, until in the opinion of the investigator the AE reaches a clinically stable outcome with or without sequelae AND the investigator and Aclaris Therapeutics, Inc. Safety and Medical Monitor agree that the SAE is satisfactorily resolved.
6. Inform the Aclaris Therapeutics, Inc. Safety Monitor of SAE updates, via telephone, followed by an SAE form update sent by e-mail.
7. Comply with the appropriate regulatory requirements and Aclaris Therapeutics, Inc. instructions regarding reporting of the SAE to the responsible Institutional Review Board (IRB) or Ethics Committee (EC).

9.2.3. Safety Monitoring Discontinuation Criteria

Any subject who develops any of the following ECG findings during the active treatment phase will be instructed to stop study medication and will be withdrawn from the study:

- A post-study medication ECG result where the evaluator's interpretation shows any of the following:
 - Clinically significant rhythm disturbance other than sinus rhythm or ectopic supraventricular rhythm (ectopic atrial rhythm)
 - Clinically significant conduction disturbance including PR >240msec, pre-excitation (delta wave and PR <120msec), second degree or higher AV block
 - New finding of QRS>120ms (if not present at screen. For example, subjects with Right Bundle Branch Block at screening would not need to be withdrawn from the study if their subsequent ECGs remained unchanged).
 - Evidence of QT-interval prolongation, defined as an increase in the QTcF interval>60ms from Visit 1
 - Acute signs of ischemia or infarction
 - Any ECG abnormality which may, in the opinion of the investigator, represent a new medical issue of concern

Site staff must perform protocol-required procedures for trial discontinuation and follow-up.

9.2.4. Study Medication Interruption and Discontinuation Criteria

9.2.4.1 Study Medication Interruption

Treatment with ATI-50002 Topical Solution should be temporarily interrupted in the event of severe adverse events considered related to ATI-50002, or in the event of one or more of the abnormal laboratory values in Table 2.

Table 2: Study Medication Interruption Criteria

Laboratory Test	Hold Study Medication if:	Resume Study Medication if:
WBC count	$< 2 \times 10^9/L$	$\geq 2.5 \times 10^9/L$
ANC	$< 1 \times 10^9/L$	$\geq 1.5 \times 10^9/L$
Lymphocyte count	$< 0.5 \times 10^9/L$	$\geq 0.75 \times 10^9/L$
Platelet count	$< 75 \times 10^9/L$	$\geq 100 \times 10^9/L$
Hemoglobin	$< 8 \text{ g/dL}$ or a decrease $> 2\text{ g/dL}$	$\geq 10 \text{ g/dL}$
AST or ALT	$> 3 \times \text{ULN}$	$< 2 \times \text{ULN}$ or within 20% of Baseline values
Serum creatinine	$> 2 \times \text{ULN}$	$< 1.5 \times \text{ULN}$ or within 10% of Baseline value

If a subject has one or more of the abnormal laboratory values noted in Table 2, the investigator or designee upon receipt and review of the central laboratory report should instruct the subject to hold study medication applications. The investigator or designee should ask the subject about symptoms, concomitant illnesses and medications and repeat the test(s) as soon as possible. The Medical Monitor must be notified of dose interruptions due to SAEs considered related to study medication or laboratory abnormalities noted in Table 2.

If the retest confirms the abnormal laboratory value, then the study medication should continue to be held followed by repeat testing once a week or sooner at the discretion of the investigator. The subject should be followed until the laboratory abnormality(s) return to normal or to baseline values.

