8.4.3. Clinical Laboratory Assessments

A qualified staff member will collect non-fasting samples for clinical laboratory analysis at screening and baseline and then monthly throughout the study. Samples will be sent to ACM Global Laboratories for analysis. Refer to the study specific laboratory manual for handling and shipping instructions. The following tests will be conducted:

Chemistry Panel	Complete Blood Count
Albumin	Hematocrit
Alkaline phosphatase	Hemoglobin
Alanine aminotransferase (ALT)	Platelet count
Aspartate aminotransferase (AST)	Red blood cell morphology
Blood urea nitrogen (BUN)	Red blood cell count
Bicarbonate	White blood cell count
Calcium	White blood cell differential
Chloride	% & absolute
Creatinine	Basophils
Glucose	Eosinophils
Lactate dehydrogenase (LDH)	Lymphocytes
Phosphorus	Monocytes
Potassium	Neutrophils
Sodium	

Total bilirubin	Urinalysis
Total protein	
Uric acid	
Total cholesterol, LDL, HDL,	
Triglycerides	
Creatine Phosphokinase (CPK)	
Screening Only	
Virology (HepB, HCV, HIV)	
Quantiferon Gold	
Total Iron Binding Capacity (TIBC)	
Serum iron	
Serum Ferritin	
T3/T4, TSH	
Serum pregnancy	

The following clinical laboratory tests: TIBC, serum iron, serum ferritin, T3/T4, TSH are drawn at screening to rule out any underlying conditions that could be causing alopecia. The results of the clinical laboratory tests will be reported on ACM Global Laboratory's standard reports. The investigator must note NCS or CS to define the clinical relevance of any result that is outside the normal range for the laboratory. The investigator must date and initial every laboratory report. The investigator or subinvestigator must review all the Screening (Visit 1) laboratory test results against the study entry criteria for each subject prior to Baseline (Visit 2). The investigator must report all laboratory results that are BOTH outside the normal range for the laboratory AND, in the opinion of the investigator, CS as medical history if found prior to the first study medication treatment or as an AE if found after the first study medication treatment begins. Throughout the study, the investigator must review all laboratory reports in a timely manner.

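### The hemoglobin row of Table 2 can require a hold and permit a restart on the same confirmed value, because the resume limit ignores the decrease trigger

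*Protocol*

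**What the plan says.** Protocol 9.2.4.1, Table 2, gives a hold limit and a resume limit for each laboratory test. For hemoglobin there are two alternative hold triggers: a value under 8 g/dL, or a drop of more than 2 g/dL. There is one resume condition: 10 g/dL or above.

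The paragraph under the table sets the sequence. It applies "If a subject has one or more of the abnormal laboratory values noted in Table 2", so either hemoglobin trigger is enough. The site holds, asks about symptoms, illnesses and medications, and retests. Then: "If the retest confirms the abnormal laboratory value, then the study medication should continue to be held", with further tests weekly or sooner. The Medical Monitor must be told of the interruption. The paragraph ends: "The subject should be followed until the laboratory abnormality(s) return to normal or to baseline values".

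The hemoglobin row does not name the reference for the drop. Nearby rules do name theirs. The AST/ALT resume cell uses "within 20% of Baseline values", the creatinine cell likewise refers to Baseline, and the QTcF rule in section 9.2.3 uses "an increase in the QTcF interval>60ms from Visit 1". Under section 8.4.3, samples are taken "for clinical laboratory analysis at screening and baseline and then monthly throughout the study", so each subject has two pre-dose values.

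**The concern.** The resume limit answers only one of the two reasons for holding. A subject held because hemoglobin fell by more than 2 g/dL may never have been below 10 g/dL, so the resume condition is already met when the hold starts. If the retest confirms the fall, the text tells the site to go on holding and the table tells it that dosing may resume.

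The initial hold, the retest and the notification are clear. What is not settled is when dosing may restart. With approximately 27 sites, two of them could act in opposite ways on the same confirmed value and each could point to the protocol. The rule governs exposure to a JAK1/3 inhibitor in subjects aged 12 and over.

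The unnamed reference adds to this, because it decides whether an unchanged value after restart counts as a new trigger.

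**Working it through.** There is no plan figure to reproduce; this is a check of whether the stated limits are compatible.

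**Inputs.** From Table 2, with B the reference hemoglobin and V the current value, both in g/dL:
- Hold if V < 8 or B − V > 2.
- Resume if V ≥ 10.

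**Overlap.** A value with V ≥ 10 cannot also be below 8, so both cells can be met only through the decrease trigger. That requires V < B − 2. Hold and resume are therefore both met when

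10 ≤ V < B − 2,

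which is possible only if B > 12. The width is (B − 2) − 10 = B − 12. Stepping through values in 0.1 g/dL increments gives the first overlap at B = 12.1 and these ranges:

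| Reference B | Values meeting hold and resume | Width B − 12 |
|---|---|---|
| 12 | none | 0 |
| 13 | 10.0 to 10.9 | 1.0 |
| 14 | 10.0 to 11.9 | 2.0 |
| 15 | 10.0 to 12.9 | 3.0 |

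The B values are illustrative. Exclusion criterion 14 sets numeric limits for neutrophils and platelets only, so no numeric hemoglobin entry limit removes the affected range.

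**Example.** B = 14.0, V = 11.5. The decrease is 14.0 − 11.5 = 2.5 > 2, so hold. A retest at 11.5 confirms it, so the text says continue holding. But 11.5 ≥ 10, so the table says resume.

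**Effect of the reference.** Suppose dosing restarts at 11.5 and the next scheduled sample is also 11.5. Measured from Baseline, the decrease is still 2.5 and a new hold is triggered. Measured from the previous visit, it is 11.5 − 11.5 = 0 and nothing happens.

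**Other hematology rows.** Resume limit divided by hold limit: WBC 2.5/2 = 1.25; ANC 1.5/1 = 1.50; lymphocytes 0.75/0.5 = 1.50; platelets 100/75 = 1.33. Each resume limit lies above its hold limit, so no value meets both.

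**Other text that might settle it.**
- The closing sentence of the paragraph says how long to follow the subject. Read as a restart condition, it would contradict the table's own resume limits. AST/ALT, for example, may restart below 2 × ULN, which is not yet normal.
- The Medical Monitor is notified but is given no stated restart decision.
- Section 9.2.4.2 discontinues permanently at hemoglobin below 6.5 g/dL or at a second value below 8 g/dL. It does not mention the decrease trigger, so repeated holds and restarts on that trigger have no stated end.

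**Check of the proposed rule.** Resume if V ≥ 10 and V ≥ B − 2, that is V ≥ max(10, B − 2). Hold is V < 8 or V < B − 2, that is V < max(8, B − 2). Since max(8, B − 2) never exceeds max(10, B − 2), no value meets both, whatever B is. At B = 14 the restart value becomes 12.0.

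**The case against.** The best defense is that the paragraph under the table leans toward caution: hold, retest, keep holding if confirmed, follow to normal or baseline. A site would have to read the resume cell alone to restart at 11.5 g/dL. This is fair as far as it goes, and a cautious site would go on holding. But the text gives that site no restart point, and the only one in the table is already met.

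Second, Baseline is the natural reference, since the other relative terms in Table 2 use it. That is reasonable, and the missing reference does not create the overlap. It still needs stating, because the ECG rule uses Visit 1 and the next-visit consequence depends on the choice.

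Third, every affected value is at least 10 g/dL, well above the 8 and 6.5 g/dL limits. Investigator review of each report, Medical Monitor notification and scheduled sampling also remain. This limits the severity but does not remove the contradiction. In the open-label extension the schedule also widens from Week 12 to Week 24, so a subject restarted around Week 12 could wait about 12 weeks for the next scheduled sample.

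Fourth, the AST/ALT and creatinine rows can overlap too. With a Baseline AST of 2.7 × ULN, a value of 3.1 × ULN exceeds 3 × ULN and is within 20% of Baseline (3.1/2.7 = 1.15). With a Baseline creatinine of 1.9 × ULN, 2.05 × ULN exceeds 2 × ULN and is within 10% (2.05/1.9 = 1.08). This is correct, but it needs a markedly abnormal Baseline. It is a reason to look at those rows in the same edit.

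Fifth, restarting exactly at B − 2 leaves almost no gap: at B = 14, 11.9 holds and 12.0 resumes. This stands as a point about the choice of margin.

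**Conclusion.** The point holds. As written, hold and resume are both satisfied for 10 ≤ V < B − 2 whenever the reference exceeds 12 g/dL, and nothing else in the protocol says which governs. The result needs only the limits in Table 2 and does not depend on which reference is meant, although the repeat-hold example assumes Baseline.

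How many subjects would fall in the band is unknown. The consequence is inconsistent restart of dosing between sites and possible hold–restart cycles. Nothing in the efficacy analysis turns on it. It should be corrected as a safety instruction; it is not a threat to the trial's conclusions.

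**What to change.** Rewrite the hemoglobin row of Table 2:
- **Hold** if below 8 g/dL, or more than 2 g/dL below Baseline (Visit 2).
- **Resume** only if 10 g/dL or higher and no more than 2 g/dL below Baseline.

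The sponsor's medical team should confirm the limits. It may prefer a restart margin tighter than 2 g/dL, to leave a gap like those in the other hematology rows. It should also decide whether repeated holds on the decrease trigger end treatment, and check the AST/ALT and creatinine rows for subjects with raised Baseline values.

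The drafting cost is one table row. The route is a protocol amendment, which needs IRB/EC approval before use (section 13.1). The sponsor has used administrative letters to clarify instructions before, but a restart limit changes when subjects may be dosed and so goes beyond the logistical or administrative changes allowed in section 13.4. No data collection or analysis changes.

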9.2.4.2 Study Medication Discontinuation

Study medication should be permanently discontinued in the event of any of the following:

- Severe infection requiring parenteral antimicrobial therapy or hospitalization
- Symptomatic herpes zoster
- Malignancy – except for non-melanoma skin cancer (SCC or BCC) not in or near the treatment area
- Anaphylactic or severe allergic reaction
- WBC Count: $< 1 \times 10^9/L$ or second occurrence of $< 2 \times 10^9/L$
- ANC: $< 0.5 \times 10^9/L$ or second occurrence of $< 1 \times 10^9/L$
- Lymphocyte count: $< 0.3 \times 10^9/L$ or second occurrence of $< 0.5 \times 10^9/L$
- Platelet count: $< 50 \times 10^9/L$ or second event of $< 75 \times 10^9/L$ - in each case, value should be confirmed by retesting before treatment discontinuation

- Hemoglobin: < 6.5 g/dL or second occurrence of < 8 g/dL - in each case, value should be confirmed by retesting before treatment discontinuation
- AST or ALT:
 - > 5 x ULN persisting for 2-weeks of study medication interruption or second event of > 5 x ULN
 - > 3 x ULN with total bilirubin > 2 x ULN or symptoms of hepatocellular injury (fatigue, nausea, vomiting, right upper quadrant pain or tenderness, fever, rash and/ or eosinophilia (>5%).
- Serum creatinine: > 2 x ULN persisting for > 2 weeks of treatment discontinuation or second occurrence of > 2 x ULN

The continued treatment of subjects who experience other serious or severe adverse events considered related to study treatment should be discussed with the Sponsor's medical monitor.

10. PREGNANCY

10.1. Definition of Women of Child Bearing Potential (WOCBP)

WOCBP includes any female who has experienced menarche and who has not undergone successful surgical sterilization (e.g., hysterectomy, bilateral tubal ligation, or bilateral oophorectomy) or is not postmenopausal. Postmenopausal is defined as ≥ 12 months with no menses without an alternative medical cause. WOCBP must have a negative serum pregnancy test at screening and a negative UPT at baseline prior to randomization.

10.2. Highly Effective Methods of Birth Control

The Investigator or subinvestigator will discuss the potential risk factors associated with pregnancy and the importance of maintaining a highly effective method of contraception throughout the study with all WOCBP (for example, those which result in a low failure rate - i.e., less than 1% per year when used consistently and correctly). All WOCBP must use a highly effective method of birth control during the study and for 30 days after the final application of study medication in a manner such that risk of failure is minimized.

Highly effective methods include:

- Combined (estrogen and progestogen containing) hormonal contraception associated with inhibition of ovulation:
 - oral
 - intravaginal
 - transdermal
- Progestogen-only hormonal contraception associated with inhibition of ovulation:
 - oral
 - injectable
 - implantable
- intrauterine device (IUD)
- intrauterine hormone-releasing system (IUS)
- vasectomized partner¹
- sexual abstinence²

¹Vasectomized partner is a highly effective birth control method provided that partner is the sole sexual partner of the WOCBP trial participant and that the vasectomized partner has received medical assessment of the surgical success.

² Sexual abstinence is considered a highly effective method only if defined as refraining from heterosexual intercourse during the entire period of risk associated with the study treatments. The reliability of sexual abstinence needs to be evaluated in relation to the duration of the clinical trial and the preferred and usual lifestyle of the subject.

WOCBP must be on a highly effective method of birth control for the following timeframes prior to study entry:

- Implants (on a stable dose for ≥ 30 days)
- Injectables (on a stable dose for ≥ 30 days)
- Patches (on a stable dose for ≥ 30 days)
- Combined oral contraceptives (on a stable dose for ≥ 30 days)
- Intrauterine devices (inserted for ≥ 30 days).

Prior to trial enrollment, WOCBP must be advised of the importance of avoiding pregnancy during trial participation and of the potential risk factors associated with pregnancy while in the study. The subject must sign an informed consent/ assent form documenting this discussion. During the trial, all WOCBP will be instructed to contact the investigator immediately if they suspect they might be pregnant (*e.g.*, missed or late menstrual period).

If a subject or investigator suspects that the subject may be pregnant prior to study medication administration, the study medication must be withheld until the results of a pregnancy test are available. If pregnancy is confirmed, the subject must not receive study medication and must be discharged from the study.

If, following study medication administration, it is determined that the subject may have been or was pregnant at the time of study medication exposure (including at least 2 days after study medication administration) the investigator must immediately notify the Aclaris Therapeutics, Inc. Medical Monitor and record the event on a pregnancy surveillance form. While not an AE or SAE, the investigator must report every pregnancy using a pregnancy surveillance form and follow the reporting procedures described for SAE reporting.

Protocol-required procedures for trial discontinuation and follow-up must be performed on the subject unless contraindicated by pregnancy (*e.g.*, x-ray studies). Other appropriate pregnancy follow-up procedures should be considered if indicated. In addition, the investigator must report to Aclaris Therapeutics, Inc.'s Medical Monitor on the pregnancy surveillance form, follow-up information regarding the course of the pregnancy, including perinatal and neonatal outcome. Infants should be followed for a minimum of six weeks.

11. STATISTICAL ANALYSES

The primary analysis will be conducted when all subjects have completed the double-blind period.

11.1. Sample Size and Power Calculations

The planned sample size is 120 subjects. Since this is the first multicenter study evaluating the effect of ATI-50002 Topical Solution in subjects with stable patchy alopecia areata, the sample size was based upon feasibility issues rather than on a formal power calculation. However, data from 120 subjects (40 per group), utilizing LOCF for missing data, provides 80% power to detect a 24-point difference in percent change from baseline in SALT score between any two treatment groups. This power computation was based upon the assumed standard deviation of 38%. Data from a previous study NCT02197455 showed that the standard deviation in percent change from baseline in the SALT score is 30.3%. The 38% standard deviation assumption used for this power computation was chosen to account for the increase in variance due to the lower baseline SALT entry criteria for this study as compared to NCT02197455.

